| | THIS STUDY INCLUDES ONLY THE INVESTIGATORS LISTED IN PRIOR SECTIONS. | 20 |
| 16. | CONFLICT OF INTEREST POLICY | 20 |
| 17. | REFERENCES | 21 |
| 18. | ATTACHMENTS | 22 |

List of Abbreviations

AE Adverse Event/Adverse Experience

| | |
|-------|---|
| CFR | Code of Federal Regulations |
| CRF | Case Report Form |
| CSOC | Clinical Study Oversight Committee |
| DCC | Data Coordinating Center |
| DHHS | Department of Health and Human Services |
| DSMB | Data and Safety Monitoring Board |
| FFR | Federal Financial Report |
| FWA | Federalwide Assurance |
| GCP | Good Clinical Practice |
| HIPAA | Health Insurance Portability and Accountability Act |
| ICF | Informed Consent Form |
| ICH | International Conference on Harmonisation |
| IRB | Institutional Review Board |
| ISM | Independent Safety Monitor |
| MOP | Manual of Procedures |
| N | Number (typically refers to participants) |
| NIH | National Institutes of Health |
| OHRP | Office for Human Research Protections |
| OHSR | Office of Human Subjects Research |
| PI | Principal Investigator |
| QA | Quality Assurance |
| QC | Quality Control |
| SAE | Serious Adverse Event/Serious Adverse Experience |
| SOP | Standard Operating Procedure |
| US | United States |

Protocol Summary

| | |
|--------------------------------------|--|
| Title | Accuracy of non-invasive, non-oscillometric blood pressure wristband |
| Short Title | Non-invasive blood pressure wristband accuracy |
| Brief Summary | In an intensive care unit patients who already have an intra-arterial blood pressure monitor in place, this wristband device will be applied and blood pressure readings compared for approximately 30 minutes. Blood pressure readings will be gathered and compared. |
| Phase | N/A |
| Objectives | The primary objective of the present investigation is to determine the accuracy of a non-invasive non-oscillometric blood pressure wristband device when compared to invasive intra-arterial blood pressure monitors. |
| Methodology | Open, single arm, pilot study |
| Endpoint | The percentage of blood pressure measurements falling within the acceptable standard deviation will be compared. |
| Study Duration | Total study duration is expected to be 1 month. |
| Participant Duration | Participant involvement duration is expected to be approximately 30 minutes. |
| Duration of IP administration | Total duration of investigational device use is 30 minutes. |
| Population | Patients admitted to the Intensive Care Unit who are already fitted with an invasive Arterial Line (A Line) are eligible for the trial, and no volunteer candidates for an A Line are requested. Sample size is expected to be approximately 15 patients. |
| Study Sites | NYU Langone Health Surgical Intensive Care Unit, Cardiovascular Intensive Care Unit, Neurologic Intensive Care Unit and NYU Langone Brooklyn Surgical Intensive Care Unit and Neurologic Intensive Care Unit |
| Number of participants | Total sample size is expected to be 15 patients. |
| Description of Study Agent/Procedure | The device is a band intended to be worn on the wrist for intermittent blood pressure measurements. The device applies no inflatable mechanics or moving parts. The wristband is watertight and can be worn as any type of bracelet. |
| Reference Therapy | The investigational wristband is being compared to an intra-arterial blood pressure monitor. |
| Key Procedures | Wristband application for 30 minutes. |
| Statistical Analysis | For each of the subjects, 10 intra-arterial blood pressure measurements will be collected and 10 wristband measurements will be collected at the same time points. |

| | |
|--|--|
| | 
Systolic and diastolic blood pressure measurements will be compared using an acceptable standard deviation of 10 mm Hg (+/-5 mm Hg). Mean arterial pressure measurements will be compared using an acceptable standard deviation of 5 mm Hg (+/- 2.5 mm Hg).
 
The percentage of blood pressure measurements falling within the acceptable standard deviation will be compared. The percentage of blood pressure measurements for each patient falling within the acceptable standard deviation will also be compared.
 |
|--|--|

Schematic of Study Design

1. Patients in the ICU with an intra-arterial blood pressure monitor already in place will be considered as subjects.
2. Verbal consent to participate will be obtained.
3. The blood pressure wristband will be applied to one wrist to allow for blood pressure measurements to be obtained and recorded. The blood pressure wristband will then be applied to the contralateral wrist for measurements. The total time of device application is expected to be approximately 30 minutes.
4. Demographics of the subject will be anonymous collected – height, weight, age, current medications, and general condition.
5. Blood pressure measurements from both the wristband and the intra-arterial blood pressure monitor will be compared.

2.1. Background Information and Relevant Literature

Hypertension is a common medical condition that increases the risk of ischemic heart disease, stroke, peripheral vascular disease, and other cardiovascular diseases. Currently the gold standard for blood pressure management is an invasive intra-arterial blood pressure monitor.

A noninvasive wristband device has been developed for measurement of intermittent blood pressure. It is intended to be work in day-to-day life by people with hypertension or other conditions where blood pressure monitoring is important.

The purpose of this study is to determine the accuracy of the non-invasive wristband device when compared to the invasive gold standard.

2.2. Name and Description of the Investigational Agent

LiveMetric has developed a wristband device for measurement of intermittent blood pressure. It does not require any action by the user other than wearing the band on the wrist. The device uses no inflatable mechanics or moving parts. The wristband is watertight and can be worn as any type of bracelet. See attachment for device image.

The wristband device meets the criteria for IDE exemption because it is a diagnostic device that:

- (i) Is noninvasive,
- (ii) Does not require an invasive sampling procedure that presents significant risk,
- (iii) Does not by design or intention introduce energy into a subject, and
- (iv) Is not used as a diagnostic procedure without confirmation of the diagnosis by another, medically established diagnostic product or procedure.

2.3. Potential Risks & Benefits

2.3.1. Known Potential Risks

The only potential risk is the possible discomfort associated with wearing the wristband device.

2.3.2. Known Potential Benefits

There is no potential benefit to participating in this study. In the future, the device may be used to benefit patients with high blood pressure or other conditions in which blood pressure monitoring is important.

3. Objectives and Purpose

3.1. Primary Objective

The primary objective of the present investigation is to determine the accuracy of a non-invasive non-oscillometric blood pressure wristband device when compared to invasive intra-arterial blood pressure monitors within the ISO-81060-2 requirements

3.2. Secondary Objectives (if applicable)

N/A

4. Study Design and Endpoints

4.1. Description of Study Design

1. A medical professional will measure simultaneous non-invasive auscultatory readings to determine the lateral difference for later adjustment of calculation accordingly. Calculation of lateral difference is provided in section (**Error! Reference source not found.**). All data from a subject shall be excluded if: i) the lateral difference of the reference systolic BP readings is more than 15 mmHg (2,00 kPa); or ii) the lateral difference of the reference diastolic BP readings is more than 10 mmHg (1,33 kPa).
2. If subject's reading is eligible, the medical professional or research personnel will place the LiveMetric wristband on the opposite limb than the one having the A-line, providing the location of the placement has intact skin.
3. During the measurement stage, BP values are simultaneously recorded from the reference invasive A-line and the LiveMetric device. In addition, other vital signs from the monitoring equipment can be collected as available (ECG, Respiratory rate, Pleth, and HR). The invasive BP values and other vital signs are captured from the Vital Signs Monitor (available in the patient's room) and the LiveMetric device. A measurement session of 30 minutes will be conducted for each subject. During the measurements, no information from the device will be provided to the investigator or study personnel. All the data will be processed and analyzed post-measurement according to the following considerations as required by the standard: only up to 10 consecutive measurements per subject will be analyzed; measurement will be made over 30 seconds of recording; consecutive meas-

urement will be considered as the next 30 seconds following at least a 60 second interval. Measurement (data points) is defined as recording or acquisition of signal from the monitor. The medical professional will take off the wristband at the end of this process.

4. All measurements will be processed and analyzed retrospectively according to the requirements of the standard (ISO 81060-2) as detailed below in section (**Error! Reference source not found.**). A 30-minute session of measurements will be conducted for each subject. All the data will be processed and analyzed post measurement according to the following considerations as required by the standard; only up to 10 consecutive measurements per subject will be analyzed; measurement will be made over 30 seconds of recording; consecutive measurement will be considered as the next 30 seconds following at least a 60 second interval.
5. All data points recoded during the first phase will be sent for processing and calibrating the algorithm. All the data points recorded during the second stage will be post processed by algorithm and results will be analyzed by an unbiased third party (bio-statistician).
6. Demographics of the subject will be anonymous collected from the electronic medical record – height, weight, age, current medications, and general condition.
7. Blood pressure measurements from both the wristband and the intra-arterial blood pressure monitor will be compared.

4.2. Study Endpoints

4.2.1. Primary Study Endpoints

The study endpoint will be the time when 10 blood pressure measurements have been obtained from a subject wearing the wristband.

5. Study Enrollment and Withdrawal

5.1. Inclusion Criteria

In order to be eligible to participate in this study, an individual must meet all of the following criteria:

1. Adult (>18 years old) ICU patient who already has an intra-arterial blood pressure measurement in place.

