5.2. Exclusion Criteria

An individual who meets any of the following criteria will be excluded from participation in this study:

1. Body habitus that precludes patients from wearing a device on their wrist
2. Subjects without normal palpable radial artery pulse, whether congenital, due to medical intervention, or otherwise
3. Subjects with wrist circumference less than 155mm or greater than 210mm
4. Subjects implanted with VAD's or other mechanical circulatory support device whether intracorporeal or extracorporeal
5. Patients that do not have an intra-arterial blood pressure line.

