9.3.3. Data Analysis

The data set will be collected for clinical investigation purposes and will be processed and analyzed according to the formulas provided in the ISO 81060-2: 2013.

The lateral difference will be calculated initially as the average difference between the readings or determination made on each limb according to Formula:

$$LD = \frac{1}{3} \times \left(\sum_{i=1}^3 P_i - \sum_{j=1}^3 P_j \right);$$

i is the index for the determination on the limb used for the sphygmomanometer-under-test determination;

j is the index for the reading on the limb used for the reference reading.

Only data within the inclusion criteria as defined in section (**Error! Reference source not found.**) will be processed for the purpose of clinical investigations.

The mean value of the errors for SYS and DIA BP, \bar{x}_n of the n individual paired determination of the LiveMetric device as determined above for all subjects, will be calculated according to Formula:

$$\bar{x}_n = \frac{1}{n} \times \sum_{j=1}^n X_1$$

and Formula:

$$S_n = \sqrt{\frac{1}{n-1} \times \sum_{j=1}^n (X_i - \bar{x}_n)^2}$$

Where;

X_1 is the error of the ith individual determination as determined in (**Error! Reference source not found.**);

n is the total number of determinations;

i is the index for the individual determination.

Mean or standard deviation outside the specified ranges above, mandate further algorithm modification until subsequent testing with new data sets done in accordance with this protocol meets the above criteria.

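### Eligibility accepts an arterial line at any site, but the placement rule cannot be followed for a leg line and no error formula removes a site difference

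*Combined protocol and SAP*

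**What the plan says.** **Eligibility.** Section 5.1 has one criterion: "Adult (>18 years old) ICU patient who already has an intra-arterial blood pressure measurement in place". The Protocol Summary says the same: "Patients admitted to the Intensive Care Unit who are already fitted with an invasive Arterial Line (A Line) are eligible for the trial". Sections 5.4 and 6.2.2 also ask only that a line be present. Section 5.2 has two items that come near the subject. One excludes "Patients that do not have an intra-arterial blood pressure line". The other excludes "Subjects without normal palpable radial artery pulse, whether congenital, due to medical intervention, or otherwise", which concerns the pulse and not where the catheter sits. No artery or limb is named in any of these.

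**Placement.** Section 4.1 step 2 tells staff to "place the LiveMetric wristband on the opposite limb than the one having the A-line". The Schematic of Study Design has the band on one wrist first and continues: "The blood pressure wristband will then be applied to the contralateral wrist for measurements".

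**Lateral difference.** Section 4.1 step 1 states: "A medical professional will measure simultaneous non-invasive auscultatory readings to determine the lateral difference for later adjustment of calculation accordingly". All of a subject's data are dropped above 15 mmHg systolic or 10 mmHg diastolic. Section 9.3.3 averages three readings per limb and subtracts; for the second limb, "j is the index for the reading on the limb used for the reference reading".

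**Error.** Section 9.3.1 takes the A-line mean ± 1 SD over the recording as the reference range. A device value inside the range scores zero; a value outside it scores its distance from the nearer limit. Section 9.3.3 then takes the mean and SD of those errors.

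**Data recorded.** Section 4.1 item 6 and section 6.2.1 list age, height, weight, medications and general condition. Line site is not listed.

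**The concern.** A patient with a leg line and normal radial pulses meets section 5.1 and fails nothing in section 5.2 on account of the line. The measurement rules then give no usable instruction. The limb opposite a leg line is the other leg, where a wristband cannot go, and the Schematic points to the wrists instead.

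If the patient is measured at the wrist, the comparison is between pressure at one arterial site and pressure at another. A difference between the sites would enter that patient's paired readings. It could be counted as device inaccuracy, or offset a real device bias of the opposite sign. With 15 patients, one or two can matter.

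The consequence goes beyond a reported percentage. Section 4.1 step 5 uses first-phase data to calibrate the algorithm, and section 9.3.3 requires the algorithm to be modified when the mean or SD is out of range. Because line site is not recorded, and section 12.4 makes the data anonymous and ends collection when the band comes off, the cause might not be traceable later.

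**Working it through.** **1. Can the rules be followed?**

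- *Arm line:* the opposite limb is the other arm, so step 2 works. The lateral difference compares two arms.
- *Leg line:* the opposite limb is a leg, so step 2 cannot be followed. The Schematic's two-wrist sequence can be, and the two passages disagree.

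**2. Does the lateral difference deal with a leg line?**

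- *Read literally,* section 9.3.3 compares the device limb with the reference limb, so one auscultatory reading would be on a leg. Section 4.1 would drop the patient above 15/10 mmHg. Smaller differences stay in unless the adjustment is made.
- *If both readings are taken on arms,* the result carries no information about an arm-to-leg difference.
- *In either case,* section 4.1 promises an adjustment, but the range and error rules in 9.3.1 and the mean and SD formulas in 9.3.3 have no term for it.

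**3. Inputs for the illustration**

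- From the plan: 15 patients (9.5); up to 10 readings each (4.1); tolerance ±5 mmHg for systolic and diastolic (9.1); more than 90% within tolerance (9.2).
- Check on the plan's own figure: 15 × 10 = 150, which agrees with the 150 measurements in section 9.5 when read as a study total.
- Assumed, because the documents give no figure: k = 2 or 3 patients with a non-arm line; a constant offset d of 5–15 mmHg; a reference half-range r of ±3 mmHg (2 and 5 also shown); no lateral-difference adjustment; a device exact at its own site.

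**4. Share of readings outside tolerance**

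Share = 10k/150, if every reading of those patients falls outside.

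- k = 2: 20/150 = 13.3%, above the 10% that section 9.2 leaves.
- k = 3: 30/150 = 20%.

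The offset needed depends on which error the tolerance is applied to, which the plan does not say.

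- Raw difference: d must exceed 5 mmHg.
- Section 9.3.1 error: the score is max(0, d − r), so d must exceed 5 + r. That is 8 mmHg for r = 3, 7 mmHg for r = 2 and 10 mmHg for r = 5.

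**5. Shift in the pooled mean, k = 3**

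- Raw difference: 3d/15. For d = 5 to 15 this is 1 to 3 mmHg.
- Section 9.3.1 error with r = 3: offsets of 5, 10 and 15 score 2, 7 and 12 mmHg. Multiplied by 3/15, these give 0.4, 1.4 and 2.4 mmHg.

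**6. Allowing for ordinary device error (raw difference, normal errors)**

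Set the device SD so that 95% of arm-line readings pass (SD 2.55 mmHg). At d = 10, 2.5% of an affected patient's readings pass.

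- One such patient: (14 × 0.95 + 1 × 0.025)/15 = 88.8% within tolerance.
- Three such patients: (12 × 0.95 + 3 × 0.025)/15 = 76.5%.

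For a device passing 98% (SD 2.15 mmHg), the figures are 91.5% with one such patient and 85.1% with two.

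**The case against.** The strongest reply is that the plan already screens out most of the harm. If step 2 is followed, a leg-line patient yields no device readings. If it is not followed, that is a deviation, and section 13.2 has the investigators decide whether the data can be used and replace the subject if not. This stands in part. However, 13.2 gives no criterion for the decision, and staff who follow the Schematic would not see a deviation.

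A reader might infer that the lateral-difference check can neither detect nor remove a site difference. The documents do not support that. Sections 4.1 and 9.3.3 speak of limbs, not arms, so a leg reading is not forbidden; if taken and applied, it could exclude or partly correct some patients. What is missing is any description of that reading and any formula that applies the adjustment.

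A reader might also infer that the 90% hypothesis fails even for a perfect wristband. That would need every reading of at least two patients to fall outside tolerance with no adjustment made. The documents give neither the number of non-arm lines nor the size or constancy of a site difference. Naming the types of ICU is not evidence of frequency. The zero-error range also absorbs small offsets: with r = 3, a 5 mmHg offset scores 2 mmHg and stays within tolerance.

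Finally, the plan defers to ISO 81060-2, whose text is not available here. Whether that standard limits the reference site cannot be checked.

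**Conclusion.** The textual gap is established. Eligibility accepts any line site, the placement rule in section 4.1 cannot be followed for a leg line, the Schematic conflicts with it, and no formula applies the lateral difference.

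The consequence is conditional. It requires that some non-arm lines are enrolled, that the site difference is large enough to pass the zero-error range where that applies, and that no adjustment is made. On those assumptions, two patients can account for 13.3% of readings outside tolerance, and three can move the pooled mean by about 0.4–2.4 mmHg (1–3 mmHg without the zero-error range). These figures show that the result is sensitive; they do not predict what will happen.

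The effect on the primary criterion in section 9.3.4 cannot be judged, because the ISO limits are not given in the documents. The change is worth making as a cheap improvement. The design is not shown to fail without it.

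**What to change.** - Amend sections 5.1 and 5.2 to require the reference arterial line in an upper limb, with the opposite wrist available for the band. This selects among lines already in place and does not bear on where a line is put.
- Reconcile the Schematic of Study Design with section 4.1 step 2 so that there is one placement rule.
- Record the line site on the CRF. Arteries within the arm may also differ, so the field is useful even after the restriction.
- Where the site can be recovered, report any lower-limb-line patient already enrolled separately, and do not count that patient toward the 15 patients and 150 readings.

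The cost is a short amendment, one CRF field and slightly more screen failures. The target of 15 patients and 150 readings does not change. If 5–30% of screened patients had a non-arm line (an assumption), the 20 to be screened in section 5.4 becomes 20/0.95 to 20/0.70, or 22–29 after rounding up. The 25 in section 9.5 becomes 27–36 on the same basis.

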9.2. Statistical Hypothesis

The hypothesis is that >90% of wristband blood pressure measurements will be within the accepted standard deviation when compared to the intra-arterial blood pressure measurements.

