9.5. Sample Size

As determined in ISO 81060-2 / 2013; a reference invasive BP monitoring equipment clinical investigation shall consist of a minimum of 15 patients. For each patient shall be a minimum of 150 valid BP measurements in the clinical investigation.

The goal sample size is 15 patients. It is expected that 25 patients will need to be screened to obtain the desired sample size.

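### No stated spread of blood pressures and only pooled success measures: an error that changes with pressure could pass, and the accuracy conclusion is not limited to the pressures sampled

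*Combined protocol and SAP*

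**What the plan says.** Section 5.1 has one inclusion criterion: "Adult (>18 years old) ICU patient who already has an intra-arterial blood pressure measurement in place". The exclusions in 5.2 cover body habitus, radial pulse, wrist size ("Subjects with wrist circumference less than 155mm or greater than 210mm"), circulatory support and absence of an arterial line. None concerns pressure level, and neither do sections 5.4, 5.6 or 9.5. The mm Hg limits elsewhere concern other things: the arm-to-arm difference (4.1), the spread within one data point (section 9) and the size of the error (9.1).

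On intended users, section 2.1 states: "It is intended to be work in day-to-day life by people with hypertension or other conditions where blood pressure monitoring is important".

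The success measures pool readings. Section 9.2 states: "The hypothesis is that >90% of wristband blood pressure measurements will be within the accepted standard deviation". Section 9.3.3 takes the mean and SD of error over all determinations, and 9.3.4 refers success to the ISO 81060-2:2013 criterion for SYS and DIA without writing out its limits. Section 9.1 adds percentages per patient, not by pressure. Section 9 also plans Bland-Altman agreement and linear regression, the latter described only as correlation.

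**The concern.** Each patient contributes one 30-minute session and at most ten readings, so coverage of the pressure range comes mainly from differences between 15 patients. The protocol leaves that coverage to chance. A device that pulls readings toward the middle of the range has small pooled error when most patients are near the middle, and large error where few or none are.

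At stake is what a positive result means. The device is described for people with hypertension or other conditions needing monitoring. As written, it could be called accurate with hypertensive pressures barely sampled, and neither the criterion nor the wording of the conclusion would reveal that.

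**Working it through.** **Inputs from the plan.** 15 patients (9.5: "a reference invasive BP monitoring equipment clinical investigation shall consist of a minimum of 15 patients"); at most ten readings each (4.1: "only up to 10 consecutive measurements per subject will be analyzed"); a 30-minute session (4.1); systolic limit ±5 mm Hg (9.1); more than 90% within it (9.2); an error of zero when the wristband lies within ±1 SD of the A-line mean, otherwise the distance to the nearer edge (9.3.1).

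**The plan's own figure.** 15 × 10 = 150, which matches the 150 in 9.5 as a study total. Section 9.5 words it per patient: "For each patient shall be a minimum of 150 valid BP measurements in the clinical investigation". That cannot be met: 150 windows of 0.5 min with 149 gaps of 1 min take 75 + 149 = 224 min. This needs reconciling separately. The 15 is taken from the standard, with no power calculation to reproduce.

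**Assumptions, since the documents give none.** The share of eligible patients with high pressure; the distribution of systolic pressure; the error model; one pressure level per patient.

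**Step 1: coverage.** With share p, P(none of 15) = (1 − p)^15, and P(at most 2) is binomial.

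| p | none | at most 2 |
|---|---|---|
| 10% | 0.21 | 0.82 |
| 20% | 0.035 | 0.40 |
| 30% | 0.005 | 0.13 |

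Few or none is likely if high pressure is uncommon in these units and unlikely if it is common.

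**Step 2: an illustrative error.** Let error = −0.2 × (SYS − 120). This is −8 at 160 and −12 at 180.

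Without random error or the zero-error band, a systolic mean of 120 and SD of 15 give an error SD of 0.2 × 15 = 3.0 and 90.4% of readings within ±5. That margin is fragile:
- If 10% of patients are at or above 140, the SD is 20/1.28 = 15.6, the error SD 3.12, and 89.1% are within ±5.
- If 20% are, the SD is 20/0.842 = 23.8, the error SD 4.75, and 70.7% are within ±5.
- At SD 15, random error of SD 1 gives a total of √(9 + 1) = 3.16 and 88.6%; random error of SD 3 gives √18 = 4.24 and 76.1%.

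The zero-error band works the other way. With an assumed half-width of 4 mm Hg, an under-reading of 8 scores as 4, inside ±5.

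**Step 3: simulation with band and noise.** 15 patients × 10 readings, the same error, within-patient error SD 3, half-width 4, 1,500 trials per row. The slope test is on the 15 patient means.

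| SYS mean / SD | between-patient error SD | meets >90% | pooled mean / SD of error | slope test significant |
|---|---|---|---|---|
| 120 / 10 | 3 | 0.87 | 0.0 / 2.1 | 0.61 |
| 120 / 10 | 5 | 0.21 | 0.0 / 3.3 | 0.25 |
| 120 / 15 | 3 | 0.65 | 0.0 / 2.5 | 0.87 |
| 120 / 15 | 5 | 0.12 | 0.0 / 3.7 | 0.50 |
| 140 / 25 | 3 | 0.02 | −2.3 / 4.1 | 0.99 |
| 140 / 25 | 5 | 0.004 | −2.5 / 5.0 | 0.88 |

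A repeat of the first row gave 0.90, hence a range of roughly 12% to 90% for the rows centred on 120. If the plan's 5 and 10 mm Hg are read as limits on the pooled mean and SD, every trial in the first four rows is inside them, and so are 99.6% and 96.5% in the last two. Wider coverage alone therefore does not make the pooled mean and SD sensitive to this error; the slope does that. For a slope of −0.1 with systolic mean 120 and SD 10 to 15, the slope test is significant in only 11% to 36% of trials.

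**The case against.** **Planned agreement analyses.** A reader might infer that an error growing with pressure would go undetected. The documents do not support that. Bland-Altman and regression are planned and can show a steep trend among the sampled pressures. What stands is narrower: no slope analysis or criterion is pre-specified, detection with 15 patients is uncertain, and neither method can verify error where there are no readings.

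**The standard.** A reader might infer that no spread is required at all, or that the plan breaches ISO 81060-2. The objective, analysis and success criterion rely on that standard, whose text is not supplied. One can say only that the protocol restates the patient and reading minimums and states no spread.

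**The example.** A reader might infer that the compressing device passes. Steps 2 and 3 show that it may or may not, depending on noise, reference width and pressure mix.

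**Scope.** The Protocol Summary calls this a pilot, section 2.1 names other conditions besides hypertension, and no claim specific to hypertensive pressures is planned. That lowers the stakes, but 9.3.4 still sets a pass/fail endpoint with an unrestricted conclusion. Section 4.1 says "All data points recoded during the first phase will be sent for processing and calibrating the algorithm" but does not describe the first-phase patients, so it cannot be concluded that calibration used a narrow range.

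**Conclusion.** The point holds in limited form. The protocol states no requirement on the spread of pressures, its success measures pool all readings, and its conclusion is not confined to the pressures observed. An error that changes with pressure could therefore satisfy the criteria.

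How likely that is cannot be fixed from the documents. Under the assumptions above, the chance of no high-pressure patient runs from 21% at 10% prevalence to 0.5% at 30%. A device reading 12 mm Hg low at 180 meets >90% in roughly 12% to 90% of trials when systolic pressure centres on 120, and in 2% or fewer at 140 / 25. The text gap itself depends on none of these assumptions. This is a worthwhile, low-cost improvement, not a fatal flaw.

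**What to change.** 1. In section 9, pre-specify for SYS and DIA the slope of signed error on A-line pressure, with its confidence interval, at patient level or allowing for clustering of readings within patient. Compute it on raw differences from the A-line mean as well as on the zero-error-band errors. Report mean error by pressure band, with the bands fixed before analysis. Give the interval prominence, because 15 patients cannot rule out a moderate slope by a non-significant test.
2. In 9.3.4, state that the accuracy conclusion applies only to the observed range of A-line SYS and DIA, and report that range.
3. If the sponsor finds that the standard sets a pressure spread, write it into the protocol so that recruitment can meet it.

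Items 1 and 2 leave enrolment unchanged; they cost a little more analysis and a narrower claim.

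An enrolment quota by pressure band is optional and is the sponsor's trade-off. At 10% prevalence, the chance of finding at least three high-pressure patients is 1 − P(at most 2) = 32% among the 20 screened in 5.4 and 46% among the 25 in 9.5, before refusals. A quota could therefore lengthen the one-month study, and three patients would estimate error in a band only roughly.
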